13.2.8 OCULAR DISCOMFORT SCORE

Ocular discomfort scores will be subjectively graded by the subjects using the Ora Calibra® Ocular Discomfort Scale at all scheduled visits. Both pre- and post-CAE® assessments will be made at Visits 1 and 5. Ocular discomfort scores will also be assessed during the CAE® exposure, immediately upon entering the chamber and every 5 minutes thereafter for the duration of the 90 minute exposure. The ocular discomfort scale ranges from 0 to 4 where 0 = no discomfort, 1 = intermittent awareness, 2 = constant awareness, 3 = intermittent discomfort, and 4 = constant discomfort.

13.2.8.1 ORA CALIBRA® OCULAR DISCOMFORT SCALE PRE-, POST-, AND NON-CAE®

Pre- and post-CAE® assessments of ocular discomfort will be made at Visits 1 and 5. Ocular discomfort will also be assessed during the non-CAE Visits 2, 3, and 4. Ocular discomfort will be summarized by treatment group, visit and time point (pre- and post-CAE®) using quantitative summary statistics. Change from baseline will be also summarized.

Pairwise two-sample t-tests will be employed to compare treatment and vehicle means at each visit and time point. The differences in means, two-sided 95% CIs for the difference in means and p-values will be reported. Wilcoxon rank sum tests will also be conducted. Analyses will be performed on the mITT population with observed data only.

Changes from baseline will be compared between treatment groups using ANCOVA models that adjust for baseline value, baseline inferior corneal staining (Ora Calibra® scale) and baseline eye dryness (VAS). The differences in means, two-sided 95% CIs for the difference in means and p-values will be reported. T-tests and Wilcoxon rank sum tests will also be conducted. Analyses will be performed on the mITT population with observed data only.

A binary clinical cure variable will be defined by visit for pre-CAE® ocular discomfort score = 0, and summarized by visit using number of subjects, frequency counts and percentages. Treatment groups will be compared pairwise with vehicle using Pearson's chi-square test or Fisher's exact test if the expected cell count is less than 5 in 25% or more of the cells. In addition, the proportion of responders will be compared between treatment groups using the Cochran-Mantel-Haenszel method stratifying by baseline ICSS (≤ 1.5 , > 1.5) and baseline eye dryness (< 60 , ≥ 60). For the Cochran-Mantel-Haenszel analysis of the combined Stage 1 and Stage 2 data, the study Stage will also be included as a stratification factor.

13.2.8.2 ORA CALIBRA® OCULAR DISCOMFORT SCALE DURING CAE® EXPOSURE

Ocular discomfort scores will be assessed every 5 minutes during the CAE® exposure. Continuous descriptive statistics, including 95% CIs, as well as changes from baseline will be summarized by treatment group, visit, and time point. The change from the 0 minutes assessment within the same visit and changes from baseline will also be summarized by treatment group, visit, and time point.

For both the ocular discomfort score and the change from 0 minutes, pairwise two-sample t-tests will be employed to compare treatment and vehicle means at each visit and time point. The differences in means, two-sided 95% CIs for the difference in means and p-values will be reported. Wilcoxon rank sum tests will also be conducted. Analyses will be performed on the mITT population with observed data only.

Changes from baseline will be compared between treatment groups using ANCOVA models that adjust for baseline value, baseline inferior corneal staining (Ora Calibra® scale) and baseline eye dryness (VAS). The differences in means, two-sided 95% CIs for the difference in means and p-values will be reported. T-tests and Wilcoxon rank sum tests will also be conducted. Analyses will be performed on the mITT population with observed data only.

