12.4.8 Planned Interim Analyses

An interim analysis will be performed when the last enrolled patient in Stage 1 completes Month 3 of the Expansion Cohort. There is no plan to stop the study for efficacy on the basis of the interim analysis. However, termination in individual dose groups due to safety, tolerability and/or futility may occur. Statistical significance will not be declared at the time of the interim analysis.

A final database lock will occur at the completion of Stage 2 and the safety, tolerability, and efficacy data from both Stage 1 and 2 will be analyzed separately and in a combined fashion to fully leverage the advantage of this two-stage study design. At the final analysis, statistical significance will be declared for two-sided p-values < 0.05.

Given the exploratory nature of the study no adjustments for multiplicity will be applied across the primary or secondary endpoints.

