8.4 Data Analysis Conventions

All data analysis will be performed by Statistics & Data Corporation (SDC) after the study is completed and the database has been locked and released for unmasking. Statistical programming and analyses will be performed using SAS® Version 9.4 or higher. Output will be provided in rich text format (RTF) for tables and portable document format (PDF) for tables, listings, and figures using landscape orientation. All study data will be listed by subject, treatment, and visit (as applicable) based on all randomized subjects unless otherwise specified.

Summaries for continuous and ordinal variables will include the number of observations (n), arithmetic mean, standard deviation (SD), median, minimum, and maximum). Minima and maxima will be reported with the same precision as the raw values; means and medians will be presented to one additional decimal place than reported in the raw values. SDs will be presented to two additional decimal places than reported in the raw values. Summaries for discrete variables will include frequency counts and percentages. All percentages will be rounded to one decimal place (i.e., XX.X%). Differences between active treatment groups and vehicle will be calculated as Active minus Vehicle and change from baseline will be calculated as follow-up visit minus baseline. The baseline measure will be defined as the last non-missing measure prior to initiation of investigational treatment.

Statistical comparisons between each AXR-159 Ophthalmic Solution group will be to the vehicle group at matched dosing frequency (TID or BID). AXR-159 Ophthalmic Solution plus Artificial Tear group will be compared to both AXR-159 Ophthalmic Solution and to the vehicle group at matched dosing frequency.

A final database lock will occur at the completion of Stage 2 and the safety, tolerability, and efficacy data from both Stage 1 and 2 will be analyzed separately and in a combined fashion to fully leverage the advantage of this two-stage study design.

All statistical tests will be two-sided with a significance level of 0.05 ($\alpha = 0.05$) unless otherwise specified. Confidence intervals (CI) for differences between treatment groups will be two-sided at 95% confidence. All p-values will be rounded to four decimal places; p-values less than 0.0001 will be presented as “<0.0001”; p-values greater than 0.9999 will be presented as “>0.9999”.

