8.5 Adjustments for Multiplicity

This is a Phase 2 study to evaluate safety, tolerability, systemic pharmacokinetics, and pharmacodynamics. All efficacy analyses will be exploratory. There will be no multiplicity adjustments for the multiple treatment groups or multiple primary endpoints.

9. Disposition of Subjects

Subject disposition will be presented in terms of the numbers and percentages of subjects who were randomized, completed the study, and discontinued from the study. Subjects who are not discontinued from the study will be considered study completers. Disposition will be summarized by treatment group and for all subjects.

The number of subjects in each of the analysis populations (mITT, mITT2, PP and Safety) will be displayed by treatment and percentages will be calculated using randomized subjects as the denominator.

The number and percentage of subjects prematurely discontinued from the study and the reasons for study discontinuation will be summarized by treatment group for all randomized subjects. The reasons for study discontinuation that will be summarized include: subject choice, AE, protocol violations, administrative reasons, sponsor termination of study, and other. A subject listing will be provided that includes the date of and reason for premature study discontinuation.

The number and percentage of subjects with major protocol deviations will be summarized by treatment group for all randomized subjects. The protocol deviations that will be summarized include: informed consent, inclusion / exclusion and randomization, test article / study drug instillation and assignment at site, improper protocol procedures at site, site's failure to report SAE / AE, visit out of window, subject's non-compliance with test article / study drug, subject's use of prohibited concomitant medication, subject's failure to follow instructions, and other. A subject listing will be provided that includes the date

of the deviation, the deviation description and the classification of whether the deviation was judged to be major or minor.

In addition, subject listings will be provided that include informed consent date, inclusion and exclusion criteria violations, and exclusions from the PP population.

10. Demographic Variables

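### In-chamber discomfort is tested at 19 time points with up to seven unadjusted tests each, and the SAP names no summary result to read first

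*SAP*

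**What the plan says.** SAP 13.2.8 has subjects grade ocular discomfort from 0 to 4 "immediately upon entering the chamber and every 5 minutes thereafter for the duration of the 90 minute exposure", which is 19 readings (0, 5, ..., 90 minutes) at each of Visits 1 and 5.

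SAP 13.2.8.2 repeats the following comparisons for every reading:

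- "For both the ocular discomfort score and the change from 0 minutes, pairwise two-sample t-tests will be employed to compare treatment and vehicle means", and for these "Wilcoxon rank sum tests will also be conducted".
- "Changes from baseline will be compared between treatment groups using ANCOVA models that adjust for baseline value", with baseline inferior corneal staining and baseline eye dryness as further covariates. A t-test and a Wilcoxon test on the same change are added.

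The section defines no session mean, AUC, repeated-measures model or key time point. In both documents AUC appears only for pharmacokinetics.

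On error control, SAP 8.4 states "All statistical tests will be two-sided with a significance level of 0.05". SAP 8.5 states "All efficacy analyses will be exploratory" and "There will be no multiplicity adjustments for the multiple treatment groups or multiple primary endpoints". Protocol 12.4.8 extends the no-adjustment statement to secondary endpoints, but also says that at the final analysis "statistical significance will be declared for two-sided p-values < 0.05". Neither document mentions repeated time points within one endpoint.

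SAP 20 lists the in-chamber tables for Stage 1, Stage 2 and combined data, and again split by baseline median and by time to CAE qualification. The Stage 1 tables form part of the interim output.

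**The concern.** The 19 readings describe one response to one provocation. The clinical question is whether the drug lowers discomfort in the chamber, and the plan answers it with a grid of correlated p-values and no rule for reading them. A reader can pick out the most favourable minute and test type. A reader who wants one answer has to choose it after seeing the data.

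The result has an audience. Under Protocol 6.1 the DRC reviews Stage 1 efficacy data before recommending Stage 2, and at the final analysis any p-value below 0.05 may be called significant. No rule says the DRC will rely on these tables, and none says how it should read them.

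**Working it through.** **Inputs.** From the documents: 19 time points; two-sided 0.05 per test; the power statement in SAP 5 (difference 0.35, SD 0.75, 93 active and 60 vehicle, 80% power, 10% dropout); Stage 2 enrolment of 60 active and 30 vehicle (the lower figure given). The documents give no effect size, SD or within-session correlation for discomfort. The standardised effect 0.35/0.75 = 0.467 is therefore borrowed from inferior corneal staining, and the correlations are assumptions shown as ranges.

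**1. The plan's own figure.** For a two-sample t-test, the noncentrality is d/√(1/n₁ + 1/n₂). With 93 v 60 it is 0.467/0.1656 = 2.82, which gives 80.0% power. The stated 80% reproduces. The evaluable numbers are the lower combined totals after dropout: 103 × 0.9 = 92.7 and 67 × 0.9 = 60.3.

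**2. Number of tests.** There are seven tests per time point: two on the score, two on change from 0 minutes (reading the Wilcoxon sentence as covering both variables) and three on change from baseline. At 0 minutes the change from 0 is always zero, so five remain. The total is 18 × 7 + 5 = 131 per active-vehicle comparison, at Visit 5, in one dataset.

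**3. Chance findings with no drug effect.** For 19 independent tests the bound is 1 − 0.95¹⁹ = 62%. Correlation lowers it. Simulating 19 equally correlated statistics gives about 34% at correlation 0.6 and 16% at 0.9 (repeat runs move these by a point or two).

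A second simulation covered the whole set: 93 v 60, scores cut to a 0-4 scale, between-visit correlation 0.5, ANCOVA on baseline value only, and 1,500 runs per scenario. Correlation was set before scores were cut to grades, which weakens it and raises the t-test rates.

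| Within-session correlation | Any of 19 score t-tests | Any of 131 tests | One test on the session mean |
|---|---|---|---|
| equal 0.5 | 43% | 80% | 4.5% |
| equal 0.7 | 32% | 76% | 5.1% |
| equal 0.9 | 21% | 66% | 5.8% |
| serial 0.80 per 5 min | 45% | 78% | 5.6% |
| serial 0.90 per 5 min | 33% | 68% | 4.5% |
| serial 0.95 per 5 min | 25% | 64% | 4.7% |

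**4. Power for a sustained effect.** With equal correlation r, the variance of the 19-point mean relative to one reading is (1 + 18r)/19. That is 0.62 at r = 0.6 and 0.91 at r = 0.9, so SD ratios of 0.788 and 0.951.

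- Stage 2 alone, 60 v 30 less 10% = 54 v 27: one time point has noncentrality 0.467/0.2357 = 1.98 and power 50%. For the mean it is 1.98/0.951 = 2.08 to 1.98/0.788 = 2.51, and power is 54% to 70%.
- Combined, 93 v 60: one time point has 80%. For the mean the noncentrality is 2.96 to 3.58, and power is 84% to 94%.

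**5. Power if the effect builds up.** Let the effect rise linearly from 0 to 0.467 SD at 90 minutes, at 54 v 27. The average effect is 0.233 SD. The mean then has about 18% to 24% power for equal correlation 0.9 to 0.6, and about 25% for serial correlation 0.90. The last time point has 50%. The ranking reverses.

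**The case against.** The plan is open about its status. All efficacy analyses are labelled exploratory, all formal hypotheses in SAP 2.5 are pre-CAE, and no stated decision rule uses in-chamber discomfort. The SAP reports every time point with differences and 95% confidence intervals, so nothing is hidden or selected. The same scale is also compared after the exposure by baseline-adjusted ANCOVA (SAP 13.2.8.1), which is one planned comparison after the provocation. These points keep the severity low. They do not supply a lead in-chamber result, and the exploratory label sits beside a rule that still declares significance at p < 0.05.

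Three stronger readings are tempting, and none is supported.

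- A reader might infer that running many tests dilutes power. It does not here: no alpha is divided, so each test has the power it would have alone. The comparison is between one reading and an average of all of them.
- A reader might infer that a chance finding among the 19 score t-tests is likely. At 16-34% it is well above 5% but still a minority outcome. More likely than not applies only to the full set of 131, many of which are t-test and Wilcoxon pairs on the same variable.
- A reader might infer that the session mean is simply better and the time-point results can go. The SAP itself analyses change from 0 minutes and subgroups by time to CAE qualification, so it allows for change during the exposure. A rising effect makes the mean the weaker test, as step 5 shows.

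**Conclusion.** The point holds as a cheap improvement of low severity. SAP 13.2.8.2 yields 131 unadjusted p-values per comparison at Visit 5 and no single answer. The false-positive risk is about 16-34% for the 19 score t-tests at equal correlation 0.6-0.9, and roughly 64-80% across all the planned tests in the scenarios simulated. A test on the session mean stays at about 5%. For a sustained effect it raises power from 50% to 54-70% (Stage 2 alone) or from 80% to 84-94% (combined).

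The test count and the absence of a summary come straight from the SAP. The percentages rest on assumed within-session correlations and on an effect size taken from corneal staining. The power gain also depends on an effect present throughout the exposure, and it is small when the correlation is near 0.9.

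**What to change.** In SAP 13.2.8.2, name one lead comparison per active-vehicle pair: an ANCOVA on the Visit 5 mean over 0-90 minutes (AUC/90, or the average treatment effect from a repeated-measures model), adjusted for the matching Visit 1 session mean, baseline ICCS and baseline eye dryness. Keep the 19 time-point differences with 95% confidence intervals as descriptive support, for example as a profile plot. State that they are not to be read as separate significance tests.

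The cost is SAP wording, one derived variable and a short rule for incomplete sessions, since SAP 8.2 imputes no secondary endpoint. A repeated-measures model would need a little more specification. Nothing changes for subjects or sites.

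The price is that an effect that builds up gradually or appears only late is averaged down. For that reason the time-point profile must stay in the report.

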13.2.9 ORA CALIBRA® OCULAR DISCOMFORT & 4-SYMPTOM QUESTIONNAIRE

Ocular discomfort and dry eye symptoms will be assessed at all scheduled visits at the subject level in regard to how both eyes feel. Both pre- and post-CAE® assessments will be made at Visits 1 and 5. The Ora Calibra® Ocular Discomfort & 4-Symptom Questionnaire will be used, which includes rating of the severity of 5 symptoms: ocular discomfort, burning, dryness, grittiness, and stinging. Each symptom rating ranges from 0 to 5, where 0 = none and 5 = worst.

Symptom scores will be summarized by visit, time point, and treatment group using quantitative summary statistics, including 95% CIs. Change from baseline will also be summarized.

Pairwise two-sample t-tests will be employed to compare treatment and vehicle means at each visit and time point. The differences in means, two-sided 95% CIs for the difference in means and p-values will be reported. Wilcoxon rank sum tests will also be conducted. Analyses will be performed on the mITT population with observed data only.

Changes from baseline will be compared between treatment groups using ANCOVA models that adjust for baseline value, baseline inferior corneal staining (Ora Calibra® scale) and baseline eye dryness (VAS). The differences in means, two-sided 95% CIs for the difference in means and p-values will be reported. T-tests and Wilcoxon rank sum tests will also be conducted. Analyses will be performed on the mITT population with observed data only.

13.2.10 VISUAL ANALOG SCALE

At every visit, subjects will be asked to rate each ocular symptom due to ocular dryness by placing a vertical mark on a horizontal line of length 100 mm to indicate the level of discomfort. 0 mm corresponds to "no discomfort" and 100 mm corresponds to "maximal discomfort." Both pre- and post-CAE® assessments will be made at Visits 1, 2, 4, and 5. Symptoms assessed are burning/stinging, itching, foreign body sensation, blurred vision, eye dryness, photophobia, and pain.

Symptom scores and the average symptom score will be summarized by visit, time point, and treatment group using quantitative summary statistics, including 95% CIs. Change from baseline will also be summarized.

Pairwise two-sample t-tests will be employed to compare treatment and vehicle means at each visit and time point. The differences in means, two-sided 95% CI for the difference in means and p-values will be reported. Wilcoxon rank sum tests will also be conducted. Analyses will be performed on the mITT population with observed data only.

Changes from baseline will be compared between treatment groups using ANCOVA models that adjust for baseline value, baseline inferior corneal staining (Ora Calibra® scale) and baseline eye dryness (VAS). The differences in means, two-sided 95% CIs for the difference in means and p-values will be reported. T-tests and Wilcoxon rank sum tests will also be conducted. Analyses will be performed on the mITT population with observed data only.

13.2.11 OCULAR SURFACE DISEASE INDEX (OSDI)

The OSDI is described in Section 13.1.5. OSDI will be assessed on both eyes at all visits. Visit 1 and 5 assessments will be pre-CAE®. OSDI will be summarized by treatment group and visit using

quantitative summary statistics. Change from baseline will be also summarized. Each individual response, subtotal scores, and total OSDI score will be presented separately.

Pairwise two-sample t-tests will be employed to compare treatment and vehicle means at each visit and time point. The differences in means, two-sided 95% CIs for the difference in means and p-values will be reported. Wilcoxon rank sum tests will also be conducted. Analyses will be performed on the mITT population with observed data only.

Changes from baseline will be compared between treatment groups using ANCOVA models that adjust for baseline value, baseline inferior corneal staining (Ora Calibra® scale) and baseline eye dryness (VAS). The differences in means, two-sided 95% CIs for the difference in means and p-values will be reported. T-tests and Wilcoxon rank sum tests will also be conducted. Analyses will be performed on the mITT population with observed data only.

A binary clinical cure variable will be defined by visit for Total OSDI < 18, and summarized by visit using number of subjects, frequency counts and percentages. Treatment groups will be compared pairwise with vehicle using Pearson's chi-square test or Fisher's exact test if the expected cell count is less than 5 in 25% or more of the cells. In addition, the proportion of responders will be compared between treatment groups using the Cochran-Mantel-Haenszel method stratifying by baseline ICSS (≤ 1.5 , > 1.5) and baseline eye dryness (< 60 , ≥ 60). For the Cochran-Mantel-Haenszel analysis of the combined Stage 1 and Stage 2 data, the study Stage will also be included as a stratification factor.

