7.3 Inclusion Criteria

1. Male or female, 18 years of age or older at screening visit
2. Provide written informed consent
3. Be willing and able to follow instructions and participate in all study assessments and visits
4. Best-corrected visual acuity (BCVA) of 20/100 or better (Snellen equivalent), using the logarithm of the minimum angle of resolution (LogMAR) in each eye at Visits 1 and 2
5. Must have patient reported history of dry eye for at least 6 months prior to Visit 1
6. Use of non-prescription artificial tears for the symptoms of DED within the 30 days preceding the screening visit and willing to suspend use of artificial tears for the study duration
7. Corneal fluorescein staining score ≥ 2 according to the Ora Calibra[®] scale in at least one region in at least one eye at the screening Visit 1 (Pre-CAE[®]) and Visit 2
8. Conjunctival redness score ≥ 1 according to the Ora Calibra[®] Conjunctival Redness for Dry Eye Scale in at least one eye at Visit 1 (Pre-CAE[®]) and Visit 2
9. Eye dryness score ≥ 40 (0-100 VAS scale in both eyes) at Visit 1 (Pre-CAE[®]) and Visit 2
10. Total Ocular Surface Disease Index (OSDI) score > 18 at Visit 1 (Pre-CAE[®]) and Visit 2
11. In the same eye at Visits 1 and 2, subjects must have:
 - a. Inferior corneal fluorescein staining score ≥ 0.5 according to the Ora Calibra[®] Corneal and Conjunctival Staining Scale for Grading of Fluorescein Staining, Pre-CAE[®] at Visit 1
 - b. Schirmer's Tear Test without anesthesia ≥ 1 and ≤ 10 mm

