12.4.6 Secondary Efficacy Analyses

Continuous secondary efficacy variables (see [Section 8.1.2](#)) and changes from baseline in these measures will be summarized as described in [Section 12.4.1](#), and analyzed by visit using ANCOVA as described for the primary efficacy analyses.

Binary clinical cure variables representing clinical cure will be defined by visit for TBUT ≥ 10 , Schirmer's test ≥ 10 mm, Total OSDI < 18 , and Ocular Discomfort Score = 0. These binary variables will be summarized as described in [Section 12.4.1](#). Additionally, within each treatment group, shift tables for complete treatment response (yes/no) in the study eye relative to baseline will be presented for each variable.

The Cochran-Mantel-Haenszel test, stratified by baseline inferior corneal staining score (ICCS, > 1.5 and ≤ 1.5) and eye dryness score (≥ 60 and < 60) will be used to compare treatments with respect to the proportion of cured patients. Pairwise comparisons will be performed for each AXR-159 treatment group versus vehicle. Two-sided confidence intervals (95%) will be provided for the differences between treatments. The confidence intervals will be constructed using the normal approximation to the binomial distribution.

The secondary efficacy analysis will use the mITT population with observed data only.

Details of additional secondary efficacy analyses will be provided in the statistical analysis plan.

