Binary clinical cure variables will be defined by visit and region for clearing (score = 0) and 1-unit improvement (change from baseline ≤ -1), and will be summarized by visit and region using number of subjects, frequency counts and percentages. Treatment groups will be compared pairwise with vehicle using Pearson's chi-square test or Fisher's exact test if the expected cell count is less than 5 in 25% or more of the cells. In addition, the proportion of responders will be compared between treatment groups using the Cochran-Mantel-Haenszel method stratifying by baseline ICSS (≤ 1.5 , > 1.5) and baseline eye dryness (< 60 , ≥ 60). For the Cochran-Mantel-Haenszel analysis of the combined Stage 1 and Stage 2 data, the study Stage will also be included as a stratification factor.

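### For absolute-threshold cure variables, the planned Cochran-Mantel-Haenszel test is valid but leaves out the baseline of the measure being tested, giving up power if that baseline is prognostic

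*SAP*

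**What the plan says.** SAP 13.2.11 sets an absolute threshold: "A binary clinical cure variable will be defined by visit for Total OSDI < 18". Cure is compared with vehicle by a chi-square or Fisher test, and then "the proportion of responders will be compared between treatment groups using the Cochran-Mantel-Haenszel method stratifying by baseline ICSS" (cut at 1.5) and baseline eye dryness (cut at 60). Stage becomes a further stratum when the two stages are combined. Baseline OSDI is not a stratum.

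For the continuous version of the same measure, the same section says "Changes from baseline will be compared between treatment groups using ANCOVA models that adjust for baseline value", together with baseline inferior staining and baseline eye dryness.

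The same pairing of tests appears in SAP 13.2.1 (Schirmer), 13.2.2 (TFBUT), 13.2.4 (redness), 13.2.6 (Oxford fluorescein), 13.2.7 (lissamine green) and 13.2.8.1 (discomfort). It also appears in 13.2.5 for every Ora Calibra region except the inferior one.

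Protocol 12.4.6 has the same test and the same two factors: "The Cochran-Mantel-Haenszel test, stratified by baseline inferior corneal staining score" and eye dryness, which "will be used to compare treatments with respect to the proportion of cured patients". It also promises 95% intervals for the difference in proportions and leaves further secondary analyses to the SAP.

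**The concern.** When cure is a fixed cut-off, the distance a patient has to travel depends on where the patient starts. Entry requires "Total Ocular Surface Disease Index (OSDI) score > 18 at Visit 1" and again at Visit 2, and no upper limit is set. A patient who enters at 20 must fall by more than 20 - 18 = 2 points to be cured; one who enters at 60 must fall by more than 60 - 18 = 42. Baseline OSDI is therefore a natural predictor of cure. It is not a randomisation stratum (SAP 4.1), so any chance imbalance in it passes into the cure comparison.

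This is separate from counting patients who already meet a threshold at entry: for OSDI no eligible patient does, and the loss of precision remains. At stake is the power of several secondary comparisons, some of them in small Stage 2 groups.

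**Working it through.** **The plan's own figure.** The only power figure is for inferior staining (SAP 5): difference 0.35, SD 0.75, 93 v 60, two-sided 0.05.

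- SE = 0.75 × √(1/93 + 1/60) = 0.1242, and 0.35 / 0.1242 = 2.818.
- Power = Φ(2.818 - 1.960) = 80.5%, or 80.0% with the noncentral t. The stated 80% is reproduced.
- The 93 and 60 are numbers after 10% dropout: 103 × 0.9 = 92.7 and 67 × 0.9 = 60.3. The smallest Stage 2 comparison becomes 60 × 0.9 = 54 v 30 × 0.9 = 27.

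No power is stated for any cure variable, so the size of this point has to come from simulation.

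**Assumptions, none of them in the documents.** Baseline OSDI is normal with mean 40 and SD 16, truncated above 18. It has correlation r with Month 3 OSDI and 0.4 with eye dryness; inferior staining is independent of it. There were 3,000 trials per setting, so the Monte Carlo SE of a power near 70% is √(0.7 × 0.3 / 3000) = 0.8 points.

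**Tests.** (a) The planned CMH test on four strata. (b) A logistic score test with the two stratum factors. (c) The same with continuous baseline OSDI added. The step from (b) to (c) isolates the effect of baseline; (a) to (b) is only a change of test.

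| Groups, cure vehicle v active | r | (a) CMH | (b) strata | (c) strata + baseline | (c) - (b) |
|---|---|---|---|---|---|
| 93 v 60, 18.5% v 36.5% | 0.3 | 67.6 | 68.5 | 69.8 | 1.3 |
| | 0.5 | 67.6 | 68.7 | 74.9 | 6.2 |
| | 0.65 | 69.5 | 70.6 | 80.0 | 9.4 |
| 54 v 27, 18.5% v 43.5% | 0.3 | 59.9 | 61.9 | 64.6 | 2.7 |
| | 0.5 | 62.5 | 64.3 | 70.6 | 6.3 |
| | 0.65 | 61.7 | 64.1 | 74.5 | 10.4 |

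**Sensitivity to the cure rate.** At 93 v 60, with a latent effect of 0.35/0.75 = 0.467 SD and likelihood-ratio tests, the gain from adding baseline was:

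| Vehicle cure | r = 0.3 | r = 0.5 | r = 0.6 | r = 0.7 |
|---|---|---|---|---|
| 5% | 1.0 | 2.8 | 2.9 | 7.0 |
| 15% | 1.9 | 4.9 | 8.5 | 13.0 |
| 30% | 2.2 | 6.5 | 10.2 | 15.5 |

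**Type I error.** In the runs at about 15% to 30% cure, the planned CMH test ran at 4.5% to 5.4%. The adjusted score test ran at 4.9% to 6.2% at 93 v 60 and 5.5% to 6.3% at 54 v 27. With 5% cure at 54 v 27, which is only 81 × 0.05 = about 4 cures in all, it rose to about 6% to 9%.

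**Equal size.** With both tests set to the same empirical size, the gain of (c) over (a) for r = 0.3, 0.5 and 0.65 was:

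- 93 v 60, 18.5% vehicle cure: 2, 6 and 9 points.
- 93 v 60, 5% vehicle cure: -1, 2 and 3 points.
- 54 v 27, 5% vehicle cure: 2, 0 and -2 points.

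**An extra CMH stratum instead.** Splitting baseline OSDI at its median within the CMH test gains about 0 points at r = 0.3, 1 to 4 at 0.5 and 3 to 6 at 0.6. It loses about 1 point at r = 0.

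**The case against.** The strongest reply is that nothing is broken. The CMH strata are the randomisation strata other than site, the SAP and protocol agree, and the test keeps its size. SAP 8.5 calls all efficacy analyses exploratory, and no power is claimed for a cure endpoint. Total OSDI change is a primary variable with its own baseline in the ANCOVA (SAP 13.1.5), so the efficient test of that measure already exists. All of this stands and limits the point to efficiency.

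Three narrower objections also stand.

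- **Scope.** A reader might infer that every cure test ignores baseline. For inferior Ora Calibra staining, baseline ICSS is itself a stratum, in two categories. Responders defined by change (Schirmer or TFBUT gain of at least 5, staining change of -1 or lower) contain baseline by construction. Eye dryness may carry part of baseline OSDI.
- **Size.** A reader might take a loss of 5 to 10 points as a property of this trial. The documents supply neither the correlation nor the cure rate, and other plausible values give anything from about zero to about 16 points.
- **Sparse data.** The adjusted test is liberal when cures are few, so it cannot simply replace the CMH test.

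The objection does not show that baseline enters the cure comparison elsewhere. The protocol's shift tables are descriptive within groups. The baseline-median subgroups (SAP 15) split the sample and use t-tests, Wilcoxon tests and ANCOVA.

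**Conclusion.** The point holds as an optional gain in precision. It covers Total OSDI < 18, Schirmer ≥ 5 and ≥ 10 mm, TFBUT ≥ 5 and ≥ 10 s, redness = 0, discomfort = 0, and staining clearance other than in the inferior Ora Calibra region.

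For OSDI at 93 v 60 with about 18% vehicle cure, omitting baseline costs about 2 points of power at r = 0.3, 5 to 6 at 0.5 and about 10 at 0.65, and possibly nothing when cures are rare. These figures rest on an assumed OSDI distribution, correlation and cure rate. Only OSDI was simulated, so the other measures have no figure.

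The documents do not support reading this as bias, an inflated error rate or a departure from the protocol. The 80% power stated for inferior staining is unaffected.

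**What to change.** Before unmasking, add one prespecified model to SAP 13.2.1, 13.2.2, 13.2.4 to 13.2.7, 13.2.8.1 and 13.2.11, for the variables listed in the verdict:

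- **Model.** Logistic regression of cure on treatment, the ICSS and eye-dryness strata (plus Stage in the combined data) and the continuous baseline value of the same measure.
- **Status.** Report it beside the planned CMH test, which is kept.
- **Sparse data.** Fit it only where the total number of cures reaches a minimum fixed in advance, or use a small-sample-corrected test. A rule that applies when the model fails to fit would leave the choice of test to the data. About 4 cures in all is clearly too few.
- **Estimate.** Report a model-standardised risk difference with its 95% interval, so that the adjusted result is on the scale of the interval promised in Protocol 12.4.6.

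Protocol 12.4.6 leaves additional secondary analyses to the SAP, so an entry in the SAP's revision history should be enough. No new data are needed, since each baseline value is already a covariate in the matching ANCOVA. The cost is a little SAP text and programming, a second p-value per comparison, and slight liberality in small samples.
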